7.3.2.1. Overall Summary of AEs

An overview of TEAEs will be presented showing the number of TEAEs and the number and percentage of patients who:

- Experienced any TEAE
- Discontinued study drug due to an AE
- Experienced an AE considered related to study drug
- Experienced an AE considered not related to study drug
- Experienced a TEAE by each toxicity grade: Grades 1 to 5
- Experienced a TEAE leading to death

These statistics will be prepared for all TEAEs and, separately, for TESAEs (except toxicity grade) and non-serious TEAEs.

Additional overall summary tables by age, sex, race and region will also be provided.

7.3.2.2. AEs and SAEs by System Organ Class (SOC) and Preferred Term (PT)

The number of TEAEs/TESAEs and the number and percentage of patients with events will be presented by SOC and PT and by PT alone. Patients will be counted once in each SOC and PT. Percentages will be based on the total number of patients in the SS in the treatment group. The SOC's will be listed alphabetically and PT's within each SOC will be listed in order of decreasing frequency of occurrence (percentage) overall. A summary by PT alone will also be produced for events occurring in $\geq 5\%$ of patients in either treatment group.

Additional summary tables stratifying TEAEs and TESAEs by age, sex, race and region will also be provided.

The number of non-serious AEs and the number and percentage of patients with non-serious events will be presented by SOC and PT.

The incidence of TEAEs leading to study drug discontinuation, study discontinuation, and death will be summarized.

Detailed listings of patients who experience TEAEs (including PTAEs) will be presented. These listings will include seriousness, toxicity grade and relationship to treatment, as well as action

taken regarding study treatment, other action taken, and patient outcome. A separate listing of patients who discontinued from the study due to a TEAE will also be provided, as well as TEAEs resulting in death.

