**Table 2: Potential Risks and Mitigation Strategies**

Risks of Clinical Significance	Summary of Data/ Rationale for Risk	Mitigation Strategy
Identified risk		
Meningococcal infection	Patients who have not received a meningococcal vaccination within the past 5 years may be unable to receive meningococcal vaccinations prior to initiating treatment with ravulizumab during this study.	If vaccination cannot be confirmed, the patient should receive prophylactic antibiotics against meningococcal infection prior to initiating ravulizumab treatment and for at least 8 months from the final infusion of ravulizumab (only applicable to patients exposed to study drug).  When patients are vaccinated less than 2 weeks prior to treatment with ravulizumab or after initiation of ravulizumab, they should continue antibiotic prophylaxis for at least 2 weeks after meningococcal vaccination.
Potential risks		
Serious infections	Ravulizumab could increase the risk of infection in this patient population. This potential risk is based on the mode of action of ravulizumab and experience with the use of eculizumab. Since the relevance of serious infection with ravulizumab therapy has not been confirmed in clinical studies, this remains a potential risk.	Training healthcare professionals and patients about the potential risk of additional serious infection. Monitoring for signs and symptoms of serious infections will be conducted as part of routine safety assessments for this study. In addition to appropriate antibiotic coverage versus infection and opportunistic infections, guidelines for immune reconstitution and revaccination will be followed, as applicable.
Immunogenicity	Treatment with any therapeutic protein has the potential to induce an immune response. Potential clinical consequences may include severe hypersensitivity type reactions,	Across 350 patients enrolled in ravulizumab, Phase 3 clinical studies, 2 patients were reported with treatment-emergent ADAs.

Risks of Clinical Significance	Summary of Data/ Rationale for Risk	Mitigation Strategy
	decrease in efficacy and induction of autoimmunity, including antibodies to the endogenous form of the protein (Li, 2002; Casadevall, 2002).	Presence of anti-ALXN1210 antibodies will be assessed.

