7.3.2. Adverse Events (AEs)

The AEs will be coded by primary System Organ Class (SOC) and Preferred Term (PT) using MedDRA (version 23.0 or higher).

For the purposes of this SAP, only Treatment-Emergent Adverse Events (TEAEs) will be summarized. TEAEs are AEs that onset on or after Day 1 in the study. Both tabular outputs and listings will be created for TEAEs as described in this SAP; additional details regarding AEs are outlined in [Appendix 9.4.7](#).

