7.4. Interim Analysis

The primary null hypothesis that is being tested is that there is no difference in survival between 2 treatment groups (ravulizumab + BSC and BSC alone) as measured by the difference in the proportions surviving at Day 29 between the 2 treatment groups.

The alternative hypothesis is that ravulizumab + BSC will improve survival by 20% at Day 29 compared to BSC alone.

Hence, the treatment effect is $\delta = \pi_{\text{rav+BSC}} - \pi_{\text{BSC}}$, where π = proportion of patients surviving on study arm and they hypotheses are

Null hypothesis $H_0: \delta = 0$

Alternative hypothesis $H_1: \delta > 0$ (specifically 0.2).

With this treatment effect, an overall 1-sided Type I error of 0.025 and 2:1 randomization, approximately 243 patients will be required to achieve at least 90% power. Considering 10% nonevaluable subjects, a total of 270 patients will be enrolled in the study.

A pre-planned interim analysis for efficacy and futility will be conducted when approximately 50% of the information is available, that is after approximately 122 patients have completed Day 29. If the stopping criteria are met, the study may be terminated early for efficacy or futility depending on which stopping boundary is crossed.

The early stopping boundaries for efficacy and futility (non-binding) will be constructed using α -spending function as Lan-DeMets (O'Brien-Fleming) spending function, published by [Lan and DeMets \(1983\)](#) and β -spending function as Gamma(-4) that was first published by [Hwang et al \(1990\)](#).

Use of these spending functions ensures the control of Type I error to 0.025.

The p-value efficacy and futility boundaries for the interim analysis with 122 patients are 0.0016 and 0.5016. The [1-sided] p-value from the t-test statistic based on the results from combining all imputed datasets for overall inference (ie, from PROC MIANALYZE) will be compared with these stopping boundaries. The study will be terminated and ravulizumab will be declared as being statistically significant and more efficacious than BSC if the nominal [1-sided] p-value is less than 0.0016 and the study can be terminated for futility if the nominal [1-sided] p-value is greater than 0.5016.

Table 3: Stopping Boundaries

Analysis	Efficacy Boundary (p-value scale)	Futility Boundary (p-value scale)
Interim (~122 patients)	0.0016	0.5016
Final (243 patients)	0.0245	0.0245

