9.3. Sample Size, Power, and Randomization

A sample size of 243 patients (162 ravulizumab + BSC, 81 BSC alone) is required to ensure at least 90% power and detect an improvement in survival from 60% in the BSC alone group to 80% in the ravulizumab + BSC group at Day 29.

This sample size calculation was performed in EAST 6.5 and assumes:

- 1-sided Z-test of the difference in 2 proportions,
- Type I error = 0.025,
- Pooled variance,
- 2:1 randomization on the 2 treatment groups,
- One interim analysis at 50% information which will be after collecting primary efficacy data on approximately 122 patients. The early stopping boundaries for efficacy and futility (non-binding) will be constructed using α -spending function as Lan-DeMets spending function with O'Brien-Fleming flavor and β -spending function as Gamma(-4) ([Lan, 1983](#); [Hwang, 1990](#)).

Considering a nonevaluable rate of 10%, this study is planned to randomize approximately 270 patients (180 ravulizumab + BSC, 90 BSC alone).

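### Adverse events are reported only as counts and crude percentages, so a survival difference between the arms cannot be separated from a difference in toxicity

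*SAP*

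**What the plan says.** SAP 7.3.2.1 and 7.3.2.2 tabulate, by arm, the number of events and the number and percentage of patients with an event, each patient counting once per system organ class and preferred term. The denominator is fixed: "Percentages will be based on the total number of patients in the SS in the treatment group". The window opens at Day 1 and has no stated end: "TEAEs are AEs that onset on or after Day 1 in the study". SAP 5.2.1 has events collected up to the last scheduled contact, and the protocol's follow-up visits are at Days 60 and 90.

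SAP 7.3.1 summarises study duration by arm, including for the Safety Set, but nothing uses it as a denominator for events. Neither document specifies an event rate per patient-time, a time-to-first-event analysis or a cause-specific hazard for adverse events.

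The safety objective (Protocol section 3, Table 3) is comparative, and its endpoint is the incidence of treatment-emergent and serious events. SAP 7.3 plans no formal safety test. Protocol Table 2 lists serious infection as a potential risk: "Ravulizumab could increase the risk of infection in this patient population". The design aims to "detect an improvement in survival from 60% in the BSC alone group to 80% in the ravulizumab + BSC group at Day 29" (SAP 9.3).

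**The concern.** A patient who dies can have no further non-fatal event. If fewer ravulizumab patients die, that arm accumulates more days in which an event can occur. A crude percentage then mixes the event hazard with the length of time at risk. Part of any excess of infections on ravulizumab could reflect longer survival rather than toxicity, and the planned tables give a reader no means of telling the two apart.

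The SAP recognises this problem for efficacy. Sections 4.1, 4.2 and 7.2.2 set out how death is handled for ventilator-free, ICU and hospital days, SOFA, SpO2/FiO2 and progression to dialysis. The adverse event tables have no counterpart. Because safety is descriptive, the side-by-side percentages are the main planned evidence on comparative harm.

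**Working it through.** **Inputs.** From the documents: Day 29 survival of 60% (BSC) and 80% (ravulizumab); 162 + 81 evaluable and 180 + 90 randomized patients (SAP 9.3). Assumed, because the documents give none: event rates on BSC of 10%, 30% and 50%; the same event hazard *a* in both arms; the timing of deaths; discharge rates.

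**1. The plan's own figure.** For a fixed design with pooled variance, one-sided 0.025, 90% power and 2:1 allocation, the pooled proportion is (0.6 + 2×0.8)/3 = 0.733, and

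n(BSC) = [1.960×√(0.1956×1.5) + 1.282×√(0.24 + 0.16/2)]² / 0.20² = 79.8, so 80, total 240.

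The stated 243 is slightly larger, as expected with one interim look. Power at 162 + 81 is 0.904, and 243/0.9 = 270. The survival assumption therefore does drive the stated size.

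**2. Time alive to Day 29.** With constant death hazard h = −ln(S)/29, h is 0.01761 (BSC) and 0.00769 (ravulizumab) per day. Mean days alive = (1−S)/h = 22.7 and 26.0, ratio 1.145.

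**3. Crude percentage at equal toxicity.** Proportion with a non-fatal event = a/(a+h) × [1 − exp(−29(a+h))].

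| Daily hazard a | BSC | Ravulizumab | Difference |
|---|---|---|---|
| 0.0047 | 10% | 11.4% | +1.4 points |
| 0.0162 | 30% | 34.0% | +4.0 points |
| 0.0328 | 50% | 56.0% | +6.0 points |

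If deaths are instead spread evenly over 29 days, mean days alive are 0.6×29 + 0.4×14.5 = 23.2 and 0.8×29 + 0.2×14.5 = 26.1. Treating each death as falling at day 14.5, the 30% case becomes about 33%. Hence 3 to 4 points.

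**4. Against sampling noise.** For 30% versus 34.0% in 90 and 180 patients, the standard error is √[0.326×0.674×(1/90+1/180)] = 0.0605, so z = 0.0396/0.0605 = 0.65.

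**5. Patient-time rate, same scenario.** Mean time to first event, death or Day 29 is 18.47 and 20.91 days. First-event rates are 0.300/18.47 and 0.3396/20.91, both 1.62 per 100 patient-days. The ratio is 1.00.

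**6. How far the crude excess moves (30% case).**

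| Change of assumption | BSC | Ravulizumab |
|---|---|---|
| Deaths mostly early (Weibull shape 0.5) | 30% | 35.8% |
| Deaths mostly late (Weibull shape 2) | 30% | 32.4% |
| Events only in the first 7 days | 30% | 31.0% |
| Events only in hospital; discharge hazard 0.03 (BSC) vs 0.045 (ravulizumab) per day | 30% | 28.6% |
| Every death counted as an event, 1 − S×exp(−29a) | 62.5% | 50.0% |

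**7. Whether one pooled rate is safe.** Take equal hazards confined to the first 7 days. Days alive in that week are 6.59 (BSC) and 6.81 (ravulizumab). With no deaths after Day 29, days alive to Day 90 are 22.7 + 61×0.6 = 59.3 and 26.0 + 61×0.8 = 74.8. The total-event rate ratio is (6.81/74.8)/(6.59/59.3) = 0.82: a spurious benefit. Over Day 1–15 alone, with 13.18 and 14.17 days alive, it is (6.81/14.17)/(6.59/13.18) = 0.96. Rates therefore need to be given by interval.

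**The case against.** The case for leaving the plan alone is fair. Crude incidence is the protocol's declared safety endpoint, so the SAP matches the protocol. Planned follow-up is the same in both arms, and nothing is tested. Fatal events are tabulated by arm and mortality is the primary endpoint, so the survival difference will be in view. Event counts and study duration by arm would let a reader form a rough overall rate. Further safety review is deferred to an independent committee's own analysis plan, which is not among the documents.

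Most of this stands, and it is why the crude tables should stay. It does not meet the point in full: first-event rates, rates by interval and rates for infections cannot be derived from the planned outputs.

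Four stronger readings are tempting, and the documents do not support them.

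- *Ravulizumab will show excess events without toxicity.* This needs the survival gain to occur and the hazard to persist. Step 6 shows the excess shrinking to 1 point or reversing. The reversal from counting deaths depends on classification, since Protocol 10.3.2 gives death from disease progression as an example of something that need not be a serious adverse event.
- *The excess is 7 points or more by Day 90.* A constant hazard to Day 90 with no deaths after Day 29 gives 30% versus 37.4%. But the last dose is on Day 15, and the two follow-up contacts, by telephone after discharge, are described as seeking new or worsening serious events (Protocol Table 1 footnote 5; 8.4.11). Equal daily ascertainment of all events for 90 days is not a safe assumption.
- *Cumulative incidence with death as a competing event would cure it.* With complete follow-up that estimate equals the crude proportion. The formula in step 3 is that estimate, and it returns 30% versus 34.0%.
- *A drug that shortened life would look safe.* Only its non-fatal toxicity would be understated; the deaths themselves would show.

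**Conclusion.** The point holds as a cheap improvement to reporting, not as an error that threatens a trial conclusion. The adverse event tables take no account of time at risk in a trial planned around a 20-point survival difference with a comparative safety objective. At equal toxicity, the crude excess of non-fatal events to Day 29 is about 3 to 4 points for an assumed 30% BSC rate, and 1.4 to 6.0 points for assumed rates of 10% to 50%. These figures rest on the planned survival gain, a constant event hazard while alive, and the assumed timing of deaths. For a single event type the artefact is small against sampling noise. Its direction cannot be known in advance, which is the reason to report time at risk rather than to presume a bias against ravulizumab.

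**What to change.** Keep the crude tables in SAP 7.3.2.1 and 7.3.2.2 as the protocol's incidence endpoint. Add beside them, by arm:

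- first-event and total-event rates per 100 patient-days alive and under observation, for all treatment-emergent events, serious events and the infections system organ class;
- these rates by interval, for example Day 1–15 and Day 16–29, with a period after Day 29 for serious events only;
- for serious infections, a cause-specific hazard ratio with follow-up censored at death. This allows the hazard to change over time and is not distorted merely because one arm has more deaths.

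State that the rates are read together with the crude percentages and the mortality results, and that none of them alone settles whether the arms differ in toxicity.

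The cost is a few extra tables. Event onset, Day 1, death and disposition dates are already used in SAP 7.3.1, 9.4.7 and 9.5.1, so no new data and no change in conduct are needed. The downside is that a pooled rate can over-correct when events cluster early (0.82 in step 7). Intervals reduce this but do not remove it (0.96 over Day 1–15).

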7.3.2.3. AEs and SAEs by SOC, PT, and Relationship

Summaries of TEAEs and TESAEs by relationship (related vs not related) will be provided for the patients in the ravulizumab + BSC group.

7.3.2.4. AEs by SOC, PT, and Toxicity Grade

Summaries of TEAEs by toxicity grade (Grades 1 to 5) will be provided.

7.3.2.5. Other Significant Adverse Events

A by-patient listing of TEAEs of special interest (meningococcal infections) will be provided.

7.3.3. Other Safety

Other safety parameters will be summarized by treatment group for all patients in the SS where available. All data will be presented in by-patient listings.

7.3.3.1. Analyses for Laboratory Tests

Each laboratory parameter will be summarized by treatment group and visit and by site, as applicable. Changes from baseline will be presented. An overall shift table will also be summarized by visit. All laboratory values will be classified as normal, below normal, or above normal based on normal ranges supplied by the local laboratory.

7.3.3.2. Vital Signs

Vital signs (SBP, DBP, temperature, respiratory rate, and HR)) and body weight (kg), and changes from baseline in vital signs and body weight will be summarized by treatment group and visit and in by-patient listings.

7.3.3.3. Other Safety Parameters of Special Interest

Urine and serum pregnancy tests will be summarized in by-patient listings. A listing of meningococcal vaccinations will be produced showing the medication and date of vaccination for each patient. Listings of physical examinations will also be produced.

7.3.3.3.1. Electrocardiogram (ECG)

ECG results will be summarized by treatment group and visit. Descriptive statistics will be presented for each ECG parameter (including HR, PR interval, QRS interval, QT interval, RR interval, and QTcF) value and for change from baseline. Listings of ECG results will be produced.

7.3.3.3.2. Immunogenicity

For assessment of immunogenicity, the presence of confirmed positive ADAs will be summarized by visit for patients randomized and treated with ravulizumab. A by-patient listing

showing ADA results by visit will include positive/negative ADA, and for confirmed positive ADA samples, the ADA titer and presence of neutralizing antibodies will also be assessed.

7.4. Interim Analysis

The primary null hypothesis that is being tested is that there is no difference in survival between 2 treatment groups (ravulizumab + BSC and BSC alone) as measured by the difference in the proportions surviving at Day 29 between the 2 treatment groups.

The alternative hypothesis is that ravulizumab + BSC will improve survival by 20% at Day 29 compared to BSC alone.

Hence, the treatment effect is $\delta = \pi_{\text{rav+BSC}} - \pi_{\text{BSC}}$, where π = proportion of patients surviving on study arm and they hypotheses are

Null hypothesis $H_0: \delta = 0$

Alternative hypothesis $H_1: \delta > 0$ (specifically 0.2).

With this treatment effect, an overall 1-sided Type I error of 0.025 and 2:1 randomization, approximately 243 patients will be required to achieve at least 90% power. Considering 10% nonevaluable subjects, a total of 270 patients will be enrolled in the study.

A pre-planned interim analysis for efficacy and futility will be conducted when approximately 50% of the information is available, that is after approximately 122 patients have completed Day 29. If the stopping criteria are met, the study may be terminated early for efficacy or futility depending on which stopping boundary is crossed.

The early stopping boundaries for efficacy and futility (non-binding) will be constructed using α -spending function as Lan-DeMets (O'Brien-Fleming) spending function, published by [Lan and DeMets \(1983\)](#) and β -spending function as Gamma(-4) that was first published by [Hwang et al \(1990\)](#).

Use of these spending functions ensures the control of Type I error to 0.025.

The p-value efficacy and futility boundaries for the interim analysis with 122 patients are 0.0016 and 0.5016. The [1-sided] p-value from the t-test statistic based on the results from combining all imputed datasets for overall inference (ie, from PROC MIANALYZE) will be compared with these stopping boundaries. The study will be terminated and ravulizumab will be declared as being statistically significant and more efficacious than BSC if the nominal [1-sided] p-value is less than 0.0016 and the study can be terminated for futility if the nominal [1-sided] p-value is greater than 0.5016.

Table 3: Stopping Boundaries

Analysis	Efficacy Boundary (p-value scale)	Futility Boundary (p-value scale)
Interim (~122 patients)	0.0016	0.5016
Final (243 patients)	0.0245	0.0245

If the study is not stopped early for efficacy or futility at the interim analysis, the final primary analysis will be conducted when all patients have completed the Primary Evaluation Period, which is Day 29 (or ET). This analysis will include all efficacy, safety, and available PK/PD/immunogenicity study data for regulatory submission purposes.

7.4.1. **Independent DMC Analysis**

An independent data monitoring committee (IDMC) will be formed before study initiation. The IDMC's objectives and operational details will be defined in an IDMC Charter. The IDMC will conduct regular planned safety and efficacy reviews of study data as outlined in the IDMC SAP.

The planned interim analysis will be performed by the independent data analysis center and the IDMC SAP will describe the planned interim analyses in greater detail.

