### 9.2. Sample Size Determination

A sample size of 243 patients (162 ravulizumab + BSC, 81 BSC alone) is required to ensure at least 90% power and detect an improvement in survival from 60% in the BSC alone group to 80% in the ravulizumab + BSC group at Day 29.

This sample size calculation assumes:

- 1-sided Z-test of the difference in 2 proportions,
- Type I error = 0.025,
- Pooled variance,
- 2:1 randomization on the 2 treatment groups,

- One interim analysis at 50% information which will be after collecting primary efficacy data on approximately 122 patients. The early stopping boundaries for efficacy and futility (nonbinding) will be constructed using  $\alpha$ -spending function as Lan-DeMets spending function with O’Brien-Fleming flavor and  $\beta$ -spending function as Gamma(-4) (Lan, 1983; Hwang, 1990).

Considering a nonevaluable rate of 10%, this study is planned to randomize approximately 270 patients (180 ravulizumab + BSC, 90 BSC alone).

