### **9.5. Interim Analyses**

An interim analysis for efficacy and futility will be conducted when approximately 122 patients have completed Day 29. If the stopping criteria are met, the study may be terminated early for efficacy or futility depending on which stopping boundary is crossed. The early stopping boundaries for efficacy and futility (nonbinding) will be constructed using  $\alpha$ -spending function as Lan-DeMets (O'Brien-Fleming) spending function and  $\beta$ -spending function as Gamma (-4). A

1-sided t-test based on the results from combining all imputed datasets for overall inference will be used with an overall Type I error of 0.025.

The SAP will describe the planned interim analyses in greater detail.

Provided the study was not stopped early for efficacy or futility, the final primary analysis will be conducted when all patients have completed the Primary Evaluation Period. This analysis will include all efficacy, safety, and available PK/PD/immunogenicity study data for regulatory submission purposes. This analysis will not be considered an interim analysis.

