6.1. Intent-to-Treat (ITT) Population

The ITT population consists of all randomized patients and participants will be analyzed as randomized. The ITT population will be used for the analysis of efficacy data and is considered the primary analysis population.

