7.2.1.1. Handling of Dropouts or Missing Data

Missing survival data for the primary analysis will be imputed using a multiple imputation approach assuming the data are missing at random (MAR) and using a logistic regression model with covariates for treatment group, the randomization stratification factor, age, sex and presence of a pre-existing condition at baseline (diabetes mellitus, obesity, respiratory condition, and/or coronary artery disease). Sensitivity analyses will include:

- Worst-case scenario: missing survival data for patients randomized to ravulizumab + BSC group are imputed as death and missing survival data for patients randomized to BSC alone group are imputed as survived
- All available data: no imputation of missing data
- Best-case scenario: missing survival data for patients randomized to ravulizumab + BSC group are imputed as survived and missing survival data for patients randomized to BSC alone group are imputed as death
- Assuming death: all missing survival data is imputed as a death
- Assuming survival: all missing survival data is imputed as survived
- Delta-adjustment tipping point analysis ([O’Kelly and Ratitch, 2014](#)): this approach assumes that patients randomized to the ravulizumab + BSC group with missing survival data experience less survival, defined by an adjustment (delta), compared to patients with observed survival in the ravulizumab + BSC group; missing values for patients randomized to ravulizumab + BSC group are imputed by shifting the survival probability of the observed patients downward by delta until any positive conclusion drawn from the primary analysis is reversed; refer to [Appendix 9.5.2.1](#) for additional details

In another sensitivity analysis of the primary endpoint (ie, time to event), the patients who survive will be censored and will have a censor time that is based on the patient’s time from Day1 to the end of the Analysis Period, as described in [Appendix 9.5.1](#). A censoring indicator will be equal to 1 if the patient survived (was censored), and 0 if the patient died.

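### After an interim efficacy stop, the SAP and Protocol 9.5 no longer call for the Day 29 primary analysis in all randomised patients, although Protocol 9.4 does; the plan should always produce it.

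*SAP*

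**What the plan says.** **Trigger and boundary.** SAP 7.4 places the interim after about 122 patients have completed Day 29, with one-sided p-value boundaries of 0.0016 for efficacy and 0.5016 for non-binding futility. The final boundary is 0.0245 with 243 patients.

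**Action on crossing for efficacy.** SAP 7.4: "The study will be terminated and ravulizumab will be declared as being statistically significant and more efficacious than BSC". Earlier in the same section, and in SAP 7 and Protocol 9.5, the study *may* be terminated. Protocol 9.5.1 has the DMC recommend and the sponsor decide.

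**The all-patient analysis.** SAP 7.4 ties it to a condition: "If the study is not stopped early for efficacy or futility at the interim analysis, the final primary analysis will be conducted when all patients" (the sentence goes on to Day 29 or early termination). Protocol 9.5 does the same: "Provided the study was not stopped early for efficacy or futility, the final primary analysis will be conducted when all patients have completed" (again referring to Day 29). The introduction to SAP 7 carries the same condition. Protocol 9.4 schedules the primary analysis for the point at which everyone has finished the 4-week evaluation, with no condition. SAP 4.1 says the SAP overrides the protocol on analyses.

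**Population and later analyses.** SAP 6.1: "The ITT population consists of all randomized patients and participants will be analyzed as randomized". SAP 7 lists a final analysis after the follow-up visits, and SAP 9.5.1 repeats the survival derivations at study completion.

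**Outcome collection.** Protocol 1.3 (footnote 4) and 8.4.12 require a Day 29 telephone contact, covering survival, for patients discontinued during the Primary Evaluation Period. Protocol 8.4.10 does the same for patients discharged early.

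**Left open.** Neither document defines the interim analysis set or its data cut, names the primary estimate after an efficacy stop, or plans an estimate that allows for early stopping. SAP 7.4.1 defers further interim detail to an IDMC SAP that is not among the documents.

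**The concern.** The endpoint takes 29 days per patient and the documents mention no pause in recruitment. When the 122nd patient reaches Day 29, others will normally have been randomised and not yet be evaluable. An efficacy stop is when the trial would make its mortality claim, and three of the four relevant passages drop the analysis that would use those patients' Day 29 outcomes.

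What is at stake is the size and precision of the reported benefit, not the validity of the significance decision. An estimate taken at the moment a strict boundary is crossed is too large on average. Outcomes that the protocol already collects would partly correct it, but as written they need not enter any primary analysis.

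**Working it through.** **Inputs.** Protocol 9.2 and SAP 9.3: "1-sided Z-test of the difference in 2 proportions", "Type I error = 0.025", "Pooled variance", 2:1 allocation, 60% versus 80% survival, at least 90% power, 243 evaluable and 270 randomised. SAP 7.4: interim at about 122 patients, taken here as 81 + 41.

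**1. Reproduce the plan's figures.**
- The pooled proportion is (2 × 0.80 + 0.60)/3 = 0.7333, and 0.7333 × 0.2667 = 0.1956.
- Control n = [1.960 × √(0.1956 × 1.5) + 1.2816 × √(0.24 + 0.16/2)]² / 0.20² = (1.0615 + 0.7250)² / 0.04 = 79.8. That is 80 control and 240 in total for a fixed design. The stated 243 with one interim look is consistent with this, with group-sequential power of 90.3%.
- 243/0.9 = 270.
- Lan-DeMets O'Brien-Fleming spending at 122/243 gives an interim p of 0.00156 and a final p of 0.0245. The stated 0.0016 and 0.0245 are confirmed.

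**2. What it takes to cross.** One-sided p = 0.0016 corresponds to z = 2.948. With 60% observed control survival, the smallest difference that crosses is about 0.24, already above the design value of 0.20. A trial that stops must therefore usually show more than the assumed effect.

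**3. Estimate given a stop.** Simulation of 2,000,000 trials, unstratified, true difference 0.20:

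| Variance in Z | Trials that stop | Mean difference in the 122, given a stop |
|---|---|---|
| Pooled | 28.7% | 0.304 |
| Unpooled | 24.7% | 0.313 |

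The sample-size calculation uses pooled variance. The planned interim test divides the risk difference by its own standard error, which is closer to the unpooled row. Averaged over stopping and non-stopping trials, the estimate is 0.215 (pooled). With no true effect, 0.17% of trials stop (pooled), in line with the boundary.

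**4. Add in-progress patients.** The documents give no accrual rate, so the number in progress is an assumption. At r patients per week it is about 4r: 40 at 10 per week (40/162 = 25% of those randomised) and 120 at 30 per week (120/242 = 50%). The ceiling is 270 − 122 = 148.

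With m in-progress patients at 2:1, the mean difference is approximately (122 × 0.304 + m × 0.20)/(122 + m):
- m = 40: (37.1 + 8)/162 = 0.278
- m = 120: (37.1 + 24)/242 = 0.252

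Direct simulation agrees: 0.279 and 0.253 (pooled), 0.286 and 0.257 (unpooled). At m = 148 the pooled figure is 0.247.

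**5. Share of the excess removed (pooled).** The excess at the interim is 0.304 − 0.200 = 0.104. With 40 added, 0.079 remains (76%); with 120 added, 0.053 remains (51%). Follow-up reduces the overestimate but does not remove it.

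**6. Precision.** The standard error is √(0.16/n₁ + 0.24/n₀):
- 122 patients: √(0.16/81 + 0.24/41) = 0.088
- plus 40: √(0.16/108 + 0.24/54) = 0.077
- plus 120: √(0.16/161 + 0.24/81) = 0.063

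**7. Why the deciding p-value must be named.** After a stop with 60 in-progress patients added (pooled), the all-randomised one-sided p-value stays below 0.0245 in 99.8% of trials but below 0.0016 in only 91%. Without a stated rule, two reported p-values could appear to conflict.

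**8. Smaller true effect.** If the true difference is 0.10, about 3.5% of trials stop (pooled). The mean is then 0.302 at the interim and 0.236 with 60 patients added.

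**The case against.** The strongest reply is that the plan is inconsistent rather than exclusionary. Protocol 9.4 schedules the primary analysis without condition, the ITT set is everyone randomised, SAP 7 lists a later final analysis, and most passages say only that the study may stop. All of that stands. A reader might infer that in-progress patients are removed, or that termination sends them to an early-termination visit and loses their Day 29 status. The documents do not support this: Protocol 1.3 and 8.4.12 require a Day 29 contact even after discontinuation, so survival status should be available. What remains is that the SAP, which overrides the protocol on analyses, plans the all-patient primary analysis only for the no-stop case.

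A second reply is that overestimation at an early stop is common to group-sequential designs. This also stands: step 5 shows that half or more of the excess survives full follow-up. The omitted patients are not its main cause.

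A third is that interim detail belongs in the IDMC SAP. That may cover the data cut, but which estimate the trial reports as primary belongs in this SAP.

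A reader might also infer that the interim would take the ITT set literally, counting early deaths among in-progress patients while imputing those still alive under missing at random. The documents do not describe that: Protocol 9.2 and SAP 7.4 tie the interim to about 122 patients with primary data. It is a reason to define the interim set explicitly, and no more than that.

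**Conclusion.** The point holds as a conflict over what is analysed after an efficacy stop. Followed as written in SAP 7, SAP 7.4 and Protocol 9.5, the reported effect would rest on about 122 patients and average about 0.30 to 0.31 against a true 0.20, in the 25% to 29% of trials that stop under 60% versus 80%. Always running the Day 29 analysis in all randomised patients would bring this to about 0.28 to 0.25 and narrow the standard error from about 0.088 to between 0.077 and 0.063, if 40 to 120 patients are in progress.

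These figures assume the design survival rates, 2:1 allocation, an unstratified test and an assumed accrual rate. Type I error is not affected, and nothing here questions the boundaries or the sample size. The change is worth making because it is cheap and applies when the main claim would be made.

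**What to change.** In SAP 7, SAP 7.4 and Protocol 9.5:

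1. Reconcile the conditional wording with Protocol 9.4, and *will* with *may* be terminated.
2. Remove the no-stop condition, so that the Day 29 analysis in all randomised patients is always produced.
3. State that after an efficacy stop randomisation ends and patients already randomised continue their scheduled outcome follow-up (Days 29, 60 and 90). This concerns outcome collection only.
4. Define the interim set as patients randomised at least 29 days before the interim data cut, whatever their outcome, and state that the interim p-value (< 0.0016) from that set decides significance.
5. Report the all-randomised estimate and its confidence interval beside the interim estimate. Preferably add a stopping-adjusted estimate and interval, for example median-unbiased with stage-wise ordering, since item 2 only partly reduces the overestimate.

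Cost: wording in both documents and one rerun of the existing primary program, plus a short calculation if the adjusted estimate is adopted. No patients or visits are added. The downside is that the updated estimate will usually be less favourable than the interim one.
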